
The primary hypothesis of our study is that in DM patients the presence of CKD is associated with lower platelet inhibition compared with those without CKD after administration of ticagrelor 90 mg bid. Under the assumption of 10% absolute difference in mean PRI between CKD and non-CKD groups, with a common standard deviation of 13.0% a sample size of 37 patients per group will allow to detect a difference in platelet aggregation between the two

cohorts with a 90% power and two-sided $\alpha=0.05$ (22). Considering the two cohorts (CKD and non-CKD), 74 patients with a valid primary end point data will be needed. Assuming a 40% rate of invalid results due to hemolysis or drop-out, up to 102 patients will need to be randomized in the study. We anticipate to consent approximately 115 patients in order to reach the target number of patients. We have chosen a 10% absolute increase of PRI by VASP-P as reference value since this has been associated with a difference in clinical outcomes (43).

Statistical analysis plan

Categorical variables will be expressed as frequencies and percentages. Continuous variables will be presented as mean \pm SD or median [IQR] when appropriate. Continuous variables will be analyzed for normal distribution with the Kolmogorov-Smirnov test. Student's t-test will be used for comparison of normally distributed continuous variables. Wilcoxon test or Mann-Whitney's U test will be used for comparisons of continuous variables not following a normal distribution. An analysis of covariance (ANCOVA) method with a general linear model, using baseline variables significantly different between groups as covariates, will be used to evaluate the overall difference between groups and all between-groups comparisons, in line with other PK and PD studies (22,24). Analysis of variance (ANOVA) will be used to evaluate intragroup comparisons. In line with recommendations for cross-over study designs, treatment effects will be evaluated considering the functional parameters observed in the overall patient population after the treatment regardless of the sequence in which patients received treatment. Patients who will successfully complete at least one treatment phase of the study will be considered for comparisons. The absolute between-treatment mean differences and 95% confidence intervals will be estimated in the two groups. In order to perform an unbiased

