estimation of the treatment effect, period and sequence effects, which may occur in crossover studies, will be evaluated. A p-value <0.05 will be considered statistically significant. Statistical analysis will be performed using a SPSS v22.0 software.

Publication Strategy/Additional Information

This study will be performed at the University of Florida Health Science Center at UF Health - Division of Cardiology. Patients will be recruited and consented at the Cardiology clinics in the UF Health system. Patients will be screened by cardiology research, who will verify that all candidates meet inclusion criteria. Subjects will be identified with a number and data collection sheets will all be stored in a locked area. Data will be kept for 6 years after enrollment ends to comply with HIPAA regulations. Patients will receive a handout with the names and telephone numbers of the doctors involved in the study. Patients will sign an informed consent relating to the study. Study subjects will be identified first (months 1-18): we expect to enroll 4-5 subjects monthly and complete enrollment in 18 months (total: 82 subjects enrolled). Months 19-20 will be implied for statistical analysis and months 21-22 for manuscript preparation.

We anticipate no major problems with the described protocol since the approach is a straight forward prospective study and is based on well-established methods. However, since there is limited experience with to define platelet function in this specific subset, variability may be higher than expected and we cannot currently perform a detailed sample size calculation. We anticipate adding this to the protocol after inclusion of the study population has been completed. If the sample size after one year is estimated to be too small, additional patients will be included. This approach is in agreement with recommendations for pilot investigations (44).

Possible Discomforts and Risk

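### The sample-size section and the recruitment timeline give incompatible numbers, and 102 randomised does not deliver 90% power at the stated 40% loss

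*Combined protocol and SAP*

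**What the plan says.** Sample Size Computation and Power Analysis sizes the primary comparison: VASP-PRI on ticagrelor 90 mg, CKD against non-CKD. It assumes a 10-point difference in mean PRI, "with a common standard deviation of 13.0% a sample size of 37 patients per group", and compares the two "cohorts with a 90% power and two-sided" alpha of 0.05. It then asks for 74 patients with a valid primary result, allows for 40% invalid samples or drop-out, puts the number to be randomised at up to 102, and expects to consent about 115.

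Publication Strategy/Additional Information covers the same ground differently:

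- On timing: "Study subjects will be identified first (months 1-18"), then "we expect to enroll 4-5 subjects monthly and complete enrollment in 18 months (total: 82 subjects enrolled"), then "Months 19-20 will be implied for statistical analysis".
- On the calculation: "variability may be higher than expected and we cannot currently perform a detailed sample size calculation", followed by "We anticipate adding this to the protocol after inclusion of the study population has been completed".
- On extension: "If the sample size after one year is estimated to be too small, additional patients will be included". The next sentence appeals to recommendations for pilot investigations.

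Neither section says which of the two governs, and the word enrolled is not defined.

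**The concern.** One section reports a finished calculation and the other says none can yet be made. A calculation added after the last patient is included cannot justify the size of the trial. The timing is also at odds with itself: the decision to add patients falls at one year, before the calculation is due to exist.

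The figure of 82 matches neither the randomised nor the consented number, and the stated accrual rate reaches neither in 18 months. Anyone budgeting, monitoring or later reporting the trial cannot tell which number was the plan.

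The sample-size section has a further problem of its own. The 40% loss, the 102 randomised and the 90% power do not fit together, so its headline power is not what its own assumptions give.

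**Working it through.** **Inputs.** From the sample-size section: difference 10, SD 13, two-sided alpha 0.05, power 90%, 40% loss, 102 randomised, 115 consented. From Publication Strategy/Additional Information: 4-5 per month, 18 months, 82 enrolled. I assume the valid results split about equally between CKD and non-CKD, as the 37 per group implies.

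**1. The plan's own figure.** Normal approximation: n per group = 2 × 13² × (1.960 + 1.282)² / 10² = 35.5, so 36. The exact two-sample t test, with noncentrality 10 / (13 × √(1/n₁ + 1/n₂)) and n₁ + n₂ − 2 degrees of freedom, gives 89.6% power at 36 per group and 90.4% at 37. The stated 37 per group and 74 in total are reproduced.

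**2. From randomised to valid.** A 40% loss leaves 60%.

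- 102 × 0.6 = 61.2 valid, not 74.
- 74 / 0.6 = 123.3, so 124 must be randomised to keep 74 valid.
- 102 yields 74 only if loss is 1 − 74/102 = 27.5%.

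The text does not explain 102. Multiplying 74 by 1.4 gives 103.6, which is near but not equal, so I do not rely on that route.

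**3. Accrual.**

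- 18 × 4 = 72 and 18 × 5 = 90. The upper end is below both 102 and 115.
- 102 takes 102/5 = 20.4 to 102/4 = 25.5 months; 115 takes 23.0 to 28.75 months.
- Finishing in 18 months needs 102/18 = 5.7 or 115/18 = 6.4 per month.
- 82 is 20 below 102 and 33 below 115.

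**4. Power by scenario (t test, difference 10, SD 13).** The rows for 82 apply only if enrolment ends there.

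| Scenario | Valid results | Split | Power |
|---|---|---|---|
| Stated target | 74 | 37/37 | 90.4% |
| 102 randomised, 40% loss | 61.2 | 30/31 | 84.0% |
| 82 = randomised, 40% loss | 49.2 | 24/25 | 75.1% |
| 82 = consented (82 × 102/115 = 72.7 randomised), 40% loss | 43.6 | 22/22 | 70.3% |
| 82 = evaluable | 82 | 41/41 | 93.1% |

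With 82 randomised, 74 valid results require loss of at most 1 − 74/82 = 9.8%.

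**5. The one-year look.** If enrolled means randomised, 12 months gives 48-60 patients and, at 40% loss, about 29-36 valid results. An observed pooled SD of 13 would then have a 95% interval of 10.3-17.7 (29 patients) or 10.5-17.0 (36 patients). For 90% power the requirement is 23 per group at SD 10, 37 at SD 13 and 70 at SD 18, so the answer could move widely.

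**The case against.** The strongest reply is that the two sections do different jobs. The sample-size section sets the requirement, 74 valid results. The other, under a publication heading, gives a recruitment expectation and allows extra patients. On that reading 82 binds nobody, and if randomisation continues until 74 results are valid, 90% power holds. This largely stands. A reader might infer that the trial is planned to stop at 82 with about 75% power; the text expresses an expectation and does not say so. What remains is that it calls 82 the total at complete enrolment and schedules analysis for the following month.

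A reader might also infer that power falls below 90% whatever enrolled means. It does not: if 82 were evaluable patients, power would be about 93%. That is the least natural meaning, since validity is unknown at enrolment, and at 40% loss it would need 82/0.6 = 137 randomised, above the stated upper figure of 102. The text does not exclude it.

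The words up to could make 102 a ceiling, but the same sentence presents it as the number needed. The pilot reference does not settle matters either, because the sample-size section states a primary hypothesis with 90% power.

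On the extension, the lack of a rule or cap is mainly missing detail. Variability is the stated worry, which suggests an SD check, though the text names no parameter. Nothing says that the observed CKD difference would drive the decision, so a claim of type I error inflation has no basis in the documents.

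**Conclusion.** The point holds as an inconsistency to be reconciled, in two parts.

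First, the two sections conflict on whether a calculation exists, on the number of patients, and on a timeline that falls 12-30 patients short of 102 (102 − 90 and 102 − 72). The power loss attached to 82 is conditional on enrolment ending there and on what enrolled means; it is not the prescribed design.

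Second, and without any such condition, the sample-size section's own figures disagree: 102 randomised with 40% loss gives about 61 valid results and about 84% power, about six points below the stated 90%.

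These figures rest on the plan's difference of 10 and SD of 13, near-equal groups, and 40% read as the proportion lost. The 27% loss at which 102 would suffice is back-calculated; nothing in the documents supports it as an expected rate.

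**What to change.** 1. Delete the statements that a detailed calculation cannot be performed and will be added after inclusion, and reconcile the pilot sentence that follows with the stated 90%-power hypothesis.
2. Give one set of consented, randomised and evaluable numbers in both sections. If 102 and 40% loss are kept, restate power as about 84% with about 61 valid results. State a loss of about 27% only if the sponsor can support it from its own data. Keeping both 40% loss and 90% power would mean 124 randomised, 22 more than now.
3. Define enrolled, and replace 82 in 18 months with the matching timeline at 4-5 per month: about 20-26 months for 102 randomised or 23-29 for 115 consented. Alternatively, state and justify 5.7 (randomised) or 6.4 (consented) per month. Move the analysis and manuscript months to match.
4. Delete the one-year extension, or limit it to a single re-estimate of the within-group SD of VASP-PRI on 90 mg, with the 10-point difference fixed, no CKD versus non-CKD comparison, and a stated maximum. Because a within-group SD needs the CKD labels and the study is open-label, say who computes it and that only the SD is released.

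**Cost.** Items 1-3 with 102 kept are wording changes and add no patients; the price is a lower stated power and a longer stated timeline (or a higher stated rate). Keeping the extension may add patients, and an SD from about 29-36 results is imprecise enough to trigger an unneeded extension or miss a needed one.

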In clinical trials, the most common clinical side effects of ticagrelor were dyspnea (13.8%), headache (6.5%), cough (4.9%), dizziness (4.5%), nausea (4.3%), bradycardia (4.4%) principally. Infrequent events included intracranial hemorrhage (0.3%) and severe bradycardia requiring pacemaker insertion (0.9%). Patients considered to be at high risk of bradyarrhythmic events will be excluded. The most important adverse effect associated with the use of ticagrelor is bleeding. The risk of spontaneous bleeding with ticagrelor is 2.8% (24). However, such bleeding prevalence occurred in the setting of long-term (12-15 months) trials, while our study is limited to up to 14 ± 4 days of active treatment thus reducing the risk of bleeding complications. All clinical events described above, if they were to occur, as well as death, MI, stroke, and urgent revascularization procedure with PCI or coronary artery bypass grafting will be recorded. Bleeding data will be collected using PLATO definitions (24). Clinical events will be evaluated by a local committee, comprised of 2 faculty members (2 cardiologists), not directly involved in the research. In the event of a report of a serious adverse event (major bleeding – defined as life-threatening: fatal, symptomatic intracranial hemorrhage, leading to a drop in hemoglobin of at least 5 g/dL, significant hypotension requiring intravenous inotropes, requiring surgical intervention, or requiring transfusion of 4 or more units of blood; non-life-threatening: substantially disabling, intraocular bleeding leading to vision loss, or requiring at least 2 units of blood; thrombocytopenia $<50,000$) the local committee will meet and antiplatelet treatment management will be managed according to physician recommendation.

Definition of Adverse Events

An adverse event is any unintended or undesirable experience that occurs during the course of the clinical investigation whether or not it is considered to be therapy related. This includes any newly occurring event or previous condition that has increased in severity or frequency since the initiation of study treatment. Adverse events will be followed until resolution while the patient remains on-study. Once the patient is removed from study, events thought to be related to the study therapy will be followed until resolution or until the patient starts a new treatment regimen.

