Serious adverse events (SAE): An adverse event occurring while on study and considered related (reasonable possibility that the study treatment caused the adverse experience) to the study treatment that results in the following outcomes:

- Death
- A life-threatening adverse experience.
- A persistent or significant disability, incapacity, or is a congenital anomaly, or birth defect.
- Requires inpatient hospitalization, or prolongation of existing hospitalization.

The definition of serious adverse event also includes 'important medical event'. Medical and scientific judgment should be exercised in deciding whether expedited reporting is appropriate in other situations, such as important medical events that may not be immediately life-threatening or result in death or hospitalization but may jeopardize the patient and/or may require medical or surgical intervention to prevent one of the other outcomes listed in the

definition above. These should also usually be considered serious. Examples of such events are intensive treatment in an emergency room or at home for allergic bronchospasm; blood dyscrasias or convulsions that do not result in hospitalization; or development of drug dependency or drug abuse.

Reporting of serious adverse events

A copy of the MedWatch/AdEERs report must be faxed to AstraZeneca at the time the event is reported to the FDA. It is the responsibility of the investigator to compile all necessary information and ensure that the FDA receives a report according to the FDA reporting requirement timelines and to ensure that these reports are also submitted to AstraZeneca at the same time.

Serious adverse events that do not require expedited reporting need to be reported to AstraZeneca quarterly either as individual case reports or as line-listings. When reporting to AstraZeneca, a cover page should accompany the MedWatch/AdEERs form indicating the following:

- External Sponsored Research (ESR)
- The investigator IND number assigned by the FDA
- The investigator's name and address
- The trial name/title and AstraZeneca ESR reference number

Investigative site must also indicate, either in the SAE report or the cover page, the causality of events in relation to all study medications and if the SAE is related to disease progression, as determined by the principal investigator.

Send SAE report and accompanying cover page by way of fax to AstraZeneca's designated fax line: [contact].

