Serious adverse events that do not require expedited reporting to the FDA need to be reported to AstraZeneca preferably using the MedDRA coding language for serious adverse events.

In the case of blinded trials, AstraZeneca will request that the Sponsor either provide a copy of the randomization code/ code break information or unblind those SAEs which require expedited reporting.

All SAEs have to be reported to AstraZeneca, whether or not considered causally related to the investigational product. All SAEs will be documented. The investigator is responsible for informing the IRB and/or the Regulatory Authority of the SAE as per local requirements.

Possible benefits

The present investigation is aimed to evaluate the differences on the functional impact of CKD on platelet inhibition by ticagrelor in DM patients. This study is not designed to evaluate differences in clinical benefit. However, differences in antiplatelet profiles will perhaps prompt further investigation of the clinical implication of this difference by means of a larger scale clinical study.

Ethical and regulatory

A copy of the protocol, proposed informed consent form, other written subject information, and any proposed advertising material must be submitted to the IRB for written approval. A copy of the written approval of the protocol and informed consent form must be

received by AstraZeneca before recruitment of subjects into the study and shipment of AstraZeneca investigational product.

The investigator must submit and, where necessary, obtain approval from the IRB for all subsequent protocol amendments and changes to the informed consent document. The investigator is to notify the IRB of deviations from the protocol or serious adverse events or unanticipated problems occurring at the site and other adverse event reports received from AstraZeneca, in accordance with local procedures.

The investigator is responsible for obtaining annual IRB approval /renewal throughout the duration of the study. Copies of the investigator's reports and the IRB continuance of approval must be sent to AstraZeneca.

Labeling and storage

The label will include the following information: Facility Name, Patient Name, Dose, Prescription Number, and Dispensing Date. In addition, the drug name will be included as "Investigational Drug". The investigational drug will be stored in the Cardiovascular Research drug room. This area has limited and restricted access.

Potential Financial Risks or Benefits

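### The SAE definition requires relatedness to study treatment, while the reporting rule covers all SAEs whether or not they are related

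*Combined protocol and SAP*

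**What the plan says.** Four statements in the combined protocol and SAP bear on this.

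- **SAE definition** (Definition of Adverse Events, paragraph on serious adverse events): an SAE is "An adverse event occurring while on study and considered related (reasonable possibility that the study treatment caused the adverse experience) to the study treatment" and must result in death, a life-threatening experience, disability or congenital anomaly, or new or prolonged hospitalisation. The same section adds: "The definition of serious adverse event also includes 'important medical event".
- **Company reporting** (Reporting of serious adverse events): "All SAEs have to be reported to AstraZeneca, whether or not considered causally related to the investigational product".
- **Content of the report** (same section): the site must state "the causality of events in relation to all study medications and if the SAE is related to disease progression, as determined by the principal investigator".
- **General adverse event definition** (opening of Definition of Adverse Events): the broader term covers "any unintended or undesirable experience that occurs during the course of the clinical investigation whether or not it is considered to be therapy related".

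Separately, Possible Discomforts and Risk says that the listed side effects, "as well as death, MI, stroke, and urgent revascularization procedure with PCI or coronary artery bypass grafting will be recorded". That sentence carries no causality condition.

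**The concern.** The reporting rule expressly provides for SAEs that are not causally related, but the definition admits only related events among the four listed outcome types. A coordinator who starts from the definition would not open an SAE form for an unrelated hospitalisation. One who starts from the reporting rule would. Both texts are current.

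What is at stake is where the causality judgement sits. In the reporting section it is an entry in a report that already exists. In the definition it can decide whether there is a report at all, in which case the company would receive no SAE report on which to review that judgement. The stake is consistent safety reporting; the efficacy results do not depend on it.

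**Working it through.** No figure in the plan is at issue, so the check is to follow one event through the text. Take a patient admitted during a ticagrelor phase for a non-cardiac reason, with the admission judged unrelated to study treatment.

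1. **Is it an adverse event?** Yes. The general definition disregards cause.
2. **Is it an SAE under the definition?** No. The outcome qualifies, but the relatedness condition in "An adverse event occurring while on study and considered related (reasonable possibility that the study treatment caused the adverse experience) to the study treatment" fails.
3. **Does the important-medical-event paragraph bring it back?** No. That paragraph adds events that may fall short of the listed outcomes. It does not repeat the relatedness clause, but neither does it remove the clause from the four listed types.
4. **Does the reporting rule cover it?** By evident intent, yes: the rule disclaims causality. By its literal terms it acts on SAEs, and step 2 has said this event is not one.
5. **What does the report ask for?** Causality, and whether disease progression is involved. These entries fit most naturally with a definition that lets in unrelated events.
6. **Is it captured elsewhere?** As an adverse event, yes. It is not among the named clinical events in Possible Discomforts and Risk, which cover the listed side effects, bleeding, death, MI, stroke and urgent revascularisation. Recording an event there is in any case not the same as reporting it as an SAE.
7. **What of the FDA and IRB?** The investigator must "ensure that the FDA receives a report according to the FDA reporting requirement timelines", and "The investigator is responsible for informing the IRB and/or the Regulatory Authority of the SAE as per local requirements". Both depend on outside requirements that the documents do not reproduce, so no conclusion about those reports can be drawn.

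The definition and the reporting rule therefore cannot both be applied as written to this event.

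**Illustrative scale.** Inputs: 82 patients enrolled (Publication Strategy/Additional Information); up to 102 randomised (Sample Size Computation and Power Analysis); two phases of 7-10 days, at most 20 days in total (Research design).

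| | Smaller case | Larger case |
|---|---|---|
| Patients × days | 82 × 14 = 1,148 patient-days | 102 × 20 = 2,040 patient-days |
| Divided by 365.25 | 3.14 patient-years | 5.59 patient-years |
| Rate at which one event is expected | 1 / 3.14 = 0.32 per patient-year | 1 / 5.59 = 0.18 per patient-year |

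The rate is that of serious events judged unrelated. These are two worked cases, not bounds. Enrolling 4 per month for 18 months, for instance, gives 72 × 14 = 1,008 patient-days, or 2.76 patient-years and a rate of 0.36. The figures count treatment days, whereas the definition runs for the time on study.

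**The case against.** The strongest reply is that the two rules can be read together. The reporting rule acts on whatever the definition admits, and the terms differ: the definition speaks of study treatment, the rule of the investigational product. An SAE attributed to some other part of study treatment would then be reportable even though unrelated to ticagrelor. Important medical events, where the relatedness clause is not repeated, give the rule further scope. This stands as far as it goes: the reporting rule is not empty. But the document never draws that distinction between the terms, and an event unrelated to any study treatment would still be shut out.

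The report entries are also not conclusive. Causality across all study medications could mean which drug is implicated, and an event can be both possibly drug-related and linked to disease progression. That is fair; the entries support the broad reading without proving it.

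The open-label design adds little. Every patient receives ticagrelor at both doses, so masking the dose would not hide exposure from the person judging relatedness. The definition also does not say who makes its relatedness judgement; the principal investigator is named only for the report entries. Both points are accepted, and the conflict needs neither.

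Finally, a local committee of two cardiologists not directly involved in the research evaluates clinical events, and its meeting is triggered by a serious adverse event described in terms of major bleeding and thrombocytopenia. The committee is a safeguard, but it is not said to decide SAE status, and its trigger carries its own definition, which the proposed edit leaves alone.

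**Conclusion.** The inconsistency is real and unresolved. It touches all four listed outcome types and should be corrected, because the same unrelated serious event can be classified in two ways depending on which section staff follow.

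Its practical reach is limited. An event is affected only if it is serious, is judged unrelated, and the site follows the definition over the reporting rule. The intent to report regardless of cause is plain, and the adverse event definition and the list of recorded clinical events catch much of what matters. Treatment exposure is short, which suggests few events, but with no serious event rate in the documents no count can be given. No loss of FDA or IRB reports is claimed. The statistical analysis plan makes no use of SAE counts, and the sample size and the primary VASP-PRI comparison are unaffected.

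**What to change.** In the SAE definition, keep the first seven words of "An adverse event occurring while on study and considered related (reasonable possibility that the study treatment caused the adverse experience) to the study treatment", delete the rest of that quoted text, and let the sentence run straight on to the list of outcomes. Any adverse event on study with one of those outcomes is then an SAE, whatever its cause. Keep causality and disease progression as separate entries in the SAE report, as the reporting section already asks, and leave the rule on reporting to the company as it stands.

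The cost is one deleted clause, submitted to the IRB as the protocol requires for any amendment, and at most a few more SAE forms, notifications or line-listing entries. The protocol already allows quarterly case reports or listings for SAEs that do not need expedited reporting.
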